5.1 Overall trial design and plan - description

This trial is a randomized, double-blind, parallel, placebo-controlled trial to evaluate the efficacy and safety of two oral doses of MP1032 (150 mg bid and 300 mg bid) in adult patients with moderate-to-severe chronic plaque psoriasis.

The trial design consists of a 28-day screening period, a 12-week treatment period, and subsequently a 28-day follow-up period. Each patient will have 6 visits and unscheduled visits as needed.

Approximately 150 patients (2 × 50 patients MP1032 and 50 patients placebo) who meet the entry criteria will be randomized on Day 1 to receive either 150 mg MP1032, 300 mg MP1032 or placebo orally twice daily for 12 weeks. The administration of IMP will stop after end of study (in max. 13 weeks). Recruitment will be competitive between the sites but enrollment will be limited to 12 patients per site. A recruitment of more than 12 patients may be allowed after sponsor approval.

Safety parameter will be monitored from the signing of the informed consent form (ICF) until the last follow-up visit.

Efficacy and safety will be assessed as outlined in the trial flow chart.

5.2 Discussion of trial design, including the choice of control groups

Pre-clinical toxicology studies, a Phase I single plus multiple ascending dose trial, as well as an exploratory Phase IIa pilot trial of oral MP1032 have indicated a higher degree of safety and tolerability of the IMP compared to all currently used systemic psoriasis treatments. Moreover, a first assessment of oral MP1032's clinical efficacy in moderate-to-severe psoriasis in the preceding Phase IIa trial has shown clinically meaningful response in patients who entered the trial with a PASI score of 10-20 during six-week treatment period.

In several animal models of chronic, immune-mediated inflammatory diseases, MP1032 has been shown to have a pronounced anti-inflammatory effect.

The primary objective - to evaluate clinical efficacy and safety of MP1032 in patients with psoriasis during the 12-week treatment period and a 4-week follow up - will provide an opportunity to perform oral MP1032's clinical efficacy in moderate-to-severe psoriasis when taken for twice as long as done in Phase IIa.

On the basis of pre-clinical, Phase I and Phase IIa data, the current trial was also designed to assess the safety and tolerability of oral MP1032 over a period of 12 weeks, trying to reproduce the excellent tolerability and safety profile that was seen in Phase I and Phase IIa (up to 7 days and 6 weeks, respectively), over a longer period of time.

The extension of treatment to 12 weeks and a 4-week follow-up observation period will give the opportunity to obtain even more meaningful safety data and more comprehensive data on efficacy.

To evaluate systemic concentrations of MP1032 PK samples will be analyzed in a subgroup.

The photographic documentation will only be used for visual demonstration of efficacy. No assessments will be performed using this data.

Patients will be randomized to one of three treatment arms (MP1032 600mg, MP1032 300mg or placebo) in a blinded manner. The treatment allocation will be on a 1:1:1 ratio (50:50:50 patients). Recruitment will be competitive between the sites but enrollment per site will be limited to 12 patients (more than 12 patients needs to be approved by the sponsor).

5.3 Selection and discontinuation/withdrawal of patients

5.3.1 Selection of patients

The selection of patients is in accordance with the requirements of the national laws as well as the recommendations of the currently valid revision of the Helsinki Declaration [4] and the ICH GCP guideline [5]. Advertisement (e.g. newspaper, online portal, bus or metro) will be used only after positive approval by the responsible EC.

The trial population will consist of approx. 150 patients (planned 75 Germany and 75 Poland) with moderate-to-severe chronic plaque psoriasis. Patients must be able to provide written consent and meet all the inclusion criteria and none of the exclusion criteria.

A gender specific subdivision into groups is not necessary in this clinical trial. Male or female patients between 18 years and 70 years are eligible for this clinical trial insofar that they suffer from moderate-to-severe-psoriasis. The antipsoriatic efficacy is likewise detectable in men and women.

5.3.2 Inclusion criteria

All of the following criteria have to be met for inclusion of a patient in this trial:

1. Participants legally competent to sign and give informed consent.
2. Adult male and female patients between 18 years and 70 years with moderate-to-severe chronic plaque psoriasis (diagnosed by Investigator):
 - a) PASI score ≥ 10 - ≤ 20 at baseline
 - b) BSA score: $> 10\%$
 - c) Stable disease duration of ≥ 6 months at the initiation of IMP.
 - d) topical therapy fails to control the disease
3. Body Mass Index (BMI) between 18.5 and 34.9 kg/m².
4. Women of childbearing potential (WCBP) must have a negative serum pregnancy test at Screening (Visit 1). In addition, sexually active WCBP must agree to use adequate contraception throughout the trial (see Section 3.2 for more details on adequate contraception):
 - a) A method with less than 1% failure rate OR
 - b) Abstinence
5. Post-menopausal women with spontaneous amenorrhea for at least 12 months and women on hormonal replacement therapy (HRT). The use of hormonal replacement therapy (HRT) during the trial is permitted, however for these patients an appropriate contraception method according to Inclusion Criterion 4 must be ensured. Sterilized women may be included (see Section 3.2 for more details on sterile definition)
6. Male patients who are sexually active with a female partner and are not surgically sterile (vasectomy performed at least six months prior to treatment) must agree to inform their female sexual partner to use an acceptable form of birth control as described in the informed consent form. For females, an acceptable method (Pearl Index < 1%) would be to use implants, injectable, combined oral contraceptives, some intrauterine devices, or be postmenopausal, be surgically sterile (hysterectomy, bilateral tubal ligation, or bilateral oophorectomy)
7. In good health as judged by the investigator, based on medical history, physical examination, serum chemistry, hematology and urinalysis
8. Patients must meet the following clinical laboratory criteria:

- White blood cell count $\geq 3.5 \times 10^9/L$
- Platelet count $\geq 100 \times 10^9/L$
- Serum creatinine $\leq 1.5 \times$ upper limit of normal (ULN); estimated glomerular filtration rate $> 60 \text{ mL/min}$
- Total bilirubin $\leq 1.5 \times \text{ULN}$
- Aspartate aminotransferase (AST) and alanine aminotransferase (ALT) $\leq 2.5 \times \text{ULN}$
- Hemoglobin \geq lower limit of normal as per central laboratory reference ranges for women and men accordingly
- No coagulopathy (International Normalized Ratio [INR] < 1.5)

9. Patients agree to minimize normal sun exposure during the course of the trial
10. Patients are considered reliable and capable of adhering to the protocol (e.g. able to understand the patient information and complete diaries), visit schedule, or medication intake according to the judgment of the Investigator.

5.3.3 Exclusion criteria

Patients are to be excluded from the trial, when one or more of the following conditions are met:

1. Patients with non-plaque form of psoriasis (erythrodermic, guttate, pustular form of psoriasis). Associated psoriasis arthritis is allowed provided no other in-/exclusion criteria are influenced, no forbidden concomitant therapy is required for the well-being of the patient and there is no impact on trial objectives as determined by the Investigator.
2. Treatment with concomitant medication that may affect and provoke or aggravate psoriasis, e.g. antimalarial drugs, beta-blockers or ACE inhibitors unless on a stable dose for 3 months before IMP intake.
3. Evidence of skin conditions at the time of Screening Visit other than psoriasis that would interfere with evaluations of the effect of the IMP on psoriasis.
4. Patients with any serious medical condition, laboratory abnormality, or psychiatric illness that would prevent the patient from signing the ICF, as assessed by the investigator.
5. Pregnant or lactating women or women planning to become pregnant during the trial and / or within 28 days following the last dose of IMP.

6. Male patients planning a partner pregnancy or sperm donation during the trial including follow up period.
7. Known allergies to any ingredient of the IMP e.g. mannitol, macrophage modulators, or gelatin.
8. History or symptoms of a clinically significant illness in the four weeks before first treatment and during the trial that in the opinion of the investigator may place the patient at risk by trial participation or influence the outcome of the trial. Well controlled diseases such as hypertension, hyperlipidemia, diabetes or hypothyroidism are permitted.
9. Patients with active malignancy or history of malignancy, except for basal cell and actinic keratosis. Basal cell carcinoma of the skin or *in situ* cervical carcinoma that have been fully treated and show no evidence of recurrence are allowed.
10. Positive HIV-Antibody, HBs-Antigen or HCV-Antibody-Test at screening.
11. Previous strong sun exposure (e.g. sea holiday) within 28 days or UV treatment within 24 weeks before IMP initiation.
12. Known photo allergy and / or experienced drug-induced photo toxicity.
13. Elective (planned) hospitalization or medical intervention preventing patient from following the protocol requirements.
14. Prior treatment not adhering to Table 2.

Table 2: Prohibited medication:

Drug Class	Last Dose Prior to IMP Initiation (Washout Period)
Topical psoriasis medications (including, but not limited to corticosteroids, calcipotriene, topical vitamin D derivates, retinoids, coal tar) shampoos for scalp psoriasis containing tar	14 days
Topical immunosuppressive drugs (tacrolimus, pimecrolimus, or anthralin)	14 days
(Exception: Non-medicated emollients, moisturizers and sunscreens will be allowed)	
Systemic treatments (non-biologics): Systemic immunosuppressant agents (e.g.: methotrexate, cyclosporine, azathioprine)	28 days

Drug Class	Last Dose Prior to IMP Initiation (Washout Period)
Systemic fumarate Systemic corticosteroids	
Phototherapy or photochemotherapy / photosensitizing drugs	28 days
UVA phototherapy with or without psoralen, excimer laser	24 weeks
Systemic retinoids	12 weeks
Investigational drugs	24 weeks (systemic); 4 weeks (topical)
Anti-tumor necrosis factor (TNF) drugs: Adalimumab, Infliximab, brodalumab, Ixekizumab, etanercept,	8 weeks
Guselkumab, certolizumab pegol, golimumab,	12 weeks
Other biologics and other systemic therapies:	8 weeks
apremilast	12 weeks
Ustekinumab, alefacept, secukinumab	24 weeks
Rituximab	12 months

15. Planned use of any ultraviolet (UV) phototherapy or photochemotherapy / photosensitizing drugs during the course of the trial and within 28 days/24 weeks following the last dose of the IMP.
16. Patients with a history of chronic alcohol or drug abuse within 6 months of IMP initiation.
17. Patients with a blood pressure outside the given range of 160 mm Hg (systolic) and 95 mm Hg (diastolic)
18. Patients who are employed by MetrioPharm, contract research organization (CRO) or clinical site involved in the clinical trial.
19. Vulnerable patients (e.g. patients kept in detention).
20. Patients who are unable to communicate, read or understand the local language, or who display another condition, which, in the Investigator's opinion, makes them unsuitable for clinical trial participation.
21. Patient is institutionalized because of legal or regulatory order.

5.3.4 Restrictions during the clinical trial

A positive phototoxic signal detected in non-clinical studies could be indicative of a likely clinical phototoxic risk of MP1032, although the risk for the patients seems to be unlikely. Nevertheless, psoriasis patients participating in this trial should be advised to avoid strong sun exposure (sun bathing) and strong UV exposure (see inclusion criterion no. 9). Furthermore, the use of sunscreen will be recommended when spending an extended period of time outdoors. During the trial patients should adhere to their standard skin care regimen and may use their standard emollients/moisturizers as symptoms require but may not use treatments as precluded by the exclusion criteria. The latter requirement will be valid during the whole 12 weeks of trial duration plus the 4 weeks of follow up period.

5.3.5 Removal of patients from therapy or assessment

5.3.5.1 Criteria for discontinuing the whole clinical trial

Premature termination of a clinical trial may occur upon decision of the Sponsor, upon decision of the Investigator, by request of an authority, or because of withdrawal of positive vote by the responsible IEC. If the Investigator, the Sponsor, or the Medical Monitor becomes aware of conditions or events that suggest a possible hazard to patients, if the trial continues, the trial may be terminated after appropriate consultation between the relevant parties. The trial may also be terminated early at the Sponsor's discretion in the absence of such a finding.

Conditions that may warrant termination of the trial as a whole include, but are not limited to:

- Concerns for safety that arise within this trial or in any other trial with the IMP;
- The discovery of an unexpected, significant, or unacceptable risk to the patients enrolled in the trial;
- Failure to enroll patients at an acceptable rate;
- Ethical issues;
- Severe non-compliance;
- A decision on the part of the Sponsor to suspend or discontinue development of the drug.

5.3.5.2 Criteria for discontinuing in the case of individual patients

Patients may withdraw from the entire trial including follow-up at any time without penalty and for any reason without prejudice to his or her future medical care.

The following criteria must lead to discontinuation from the clinical trial in individual patients:

- Patient withdraws informed consent

- Pregnancy (see section 7.4)
- Severe protocol violations that result in a significant risk to the patient's safety
- Emergence of the following AEs including:
 - a) Patient reports symptoms which are considered unacceptable by the patient or the Investigator or if any serious AE occurs that is judged as at least possibly related to the IMP by the Investigator
 - b) Abnormal laboratory value(s) confirmed by repeat measurements:
 - Elevated liver transaminases (AST/ALT) $\geq 3 \times$ ULN AND elevated bilirubin total bilirubin $\geq 2 \times$ ULN
 - Elevated serum creatinine $\geq 2 \times$ ULN

The following criteria may lead to discontinuation from the clinical trial in individual patients:

- Use of prohibited concomitant medication as defined in section 5.4.5.

In all cases, the reason(s) for withdrawal, and the primary reason, must be recorded on the electronic data capture (EDC) system / electronic case report form (eCRF). If a patient is prematurely withdrawn from the IMP for any reason, the Investigator must make every effort to perform the evaluations described for the End of Treatment and Follow-up Visits. The Investigator should contact the Medical Monitor, whenever possible, to approve withdrawal of patients in advance.

If a patient withdraws consent and still agrees to undergo a final examination, it will be documented on the eCRF and the patient record.

A patient may also be withdrawn from the IMP by the Sponsor, Regulatory Authorities, or Independent Ethics Committees (IECs) / Institutional Review Boards (IRBs).

Patients who are withdrawn from the trial will be not replaced.

Protocol violation, failure to comply with the trial stipulations/poor compliance may lead to discontinuation from the clinical trial in individual patients.

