- Check concomitant therapy and adverse events
- Record vital signs
- Drug return / accountability and re-dispensation of unused kits/blister
- Diary collected and checked
- *Photographic documentation only for a subgroup (see section 5.5.1.4)*
- Urinalysis (see section 5.5.2)
- Collection of samples for determination of laboratory parameters (hematological status, clinical chemistry, urinalysis, see section 5.5.2)
- PASI (see section 5.5.1.1)

- PGA (see section 5.5.1.2)
- BSA (see section 5.5.1.3)
- Dispensing of IMP and diary

Trial Day 84 (week 12, visit 5) (EoT)

- Check concomitant therapy and adverse events
- Physical examination (see section 5.5.5)
- Record vital signs (see section 5.5.3)
- Urine pregnancy test and urinalysis (see section 5.5.2)
- *Photographic documentation only for a subgroup (see section 5.5.1.4)*
- Collection of samples for determination of laboratory parameters (hematological status, clinical chemistry, see section 5.5.2)
- *PK samples only for a subgroup (see section 5.5.1.5)*
- Last IMP administration at site for all patients
- Drug return / accountability
- Diary collected and checked
- PASI (see section 5.5.1.1)
- PGA (see section 5.5.1.2)
- BSA (see section 5.5.1.3)

Trial Day 112 (week 16, visit 6, Follow-up) (End of Study, EoS)

- *Photographic documentation only for a subgroup (see section 5.5.1.4)*
- Check concomitant therapy and adverse events
- Physical examination (see section 5.5.5)
- Record vital signs (see section 5.5.3)
- Urinalysis(see section 5.5.2)
- Collection of samples for determination of laboratory parameters (hematological status, clinical chemistry, see section 5.5.2)
- PASI (see section 5.5.1.1)
- PGA (see section 5.5.1.2)
- BSA (see section 5.5.1.3)

The patients must be present at site for approximately 60 minutes on Screening and Day 1, 45 minutes on Day 28 and 56, 60 minutes on Day 84 and 45 minutes on Day 112.

The above mentioned time will be extended for 15 minutes for patients with photographic documentation on each visit.

The above mentioned time will be extended on Day 1 and Day 84 for 120 minutes for patients with PK sampling.

Early Termination Visit

Patients who discontinue early from the trial should, if possible, have an Early Termination Visit. This visit should take place as soon as possible after the patient stops taking IMP. The observations and procedures scheduled for Visit 5 (End of Treatment) should be performed at the Early Termination Visit.

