3.1 Definitions

The following definitions apply:

- Baseline: The latest non-missing observation prior to first treatment with IMP.

Baseline data definition	obtained on/at
Age, race, height, body weight, BMI	Screening
Relevant medical history (last 5 years) including psoriasis history, relevant surgical history (last 5 years) and relevant previous medication (last 6 weeks) including psoriatic treatment taken (last 6 weeks)	Screening
Smoking and alcohol consumption	Screening
Concomitant medication	Day 1
Adverse events	Day 1
Physical examination	Day 1, Screening*
Vital signs (blood pressure, pulse rate)	Day 1, Screening*
Safety laboratory parameters	Day 1, Screening*
PASI, PGA, BSA	Day 1, Screening*

*only in case of missing Day 1 assessment

- Change from baseline = post baseline value – baseline value
- Percent change from baseline = $100 * \text{change from baseline} / \text{baseline value}$
- Last observation carried forward (LOCF): The last observed value (either scheduled or unscheduled) carried forward and used for all directly subsequent and missing scheduled points.
- Current medical conditions – medical conditions ongoing at first dosing.
- Prior therapy: Any medication or therapy taken prior to start of first IMP dosing.
- Concomitant therapy: A medication or therapy ongoing at start of first IMP dosing, or starting after the first IMP dosing.
- Treatment emergent adverse event (TEAE): Adverse event with an onset (or worsening) on or after the time of the first IMP dosing.
- Time to achievement of PASI 50 (75): Day of first visit were PASI 50 (75) is observed.
- Analysis centers: Pooled small centers for analyses, as described in section 3.5.4.

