3.5.1 Missing data

A description of missing data will be provided in the clinical study report.

For the evaluation of success rates of the primary efficacy variables PASI and PGA missing PGA assessments and/or any parts of the PASI assessments will be evaluated as failure to achieve improvement.

For descriptive analyses of PASI, PGA and BSA the last observation carried forward (LOCF) principle will be applied to impute the missing assessments, up to the Day 84 visit. Follow-up assessments will not be imputed.

Sensitivity of the primary efficacy analyses will be evaluated applying PP analyses.

Regarding incomplete recordings for adverse events the following rules apply:

- For start and stop dates no imputation will be applied. If any, start or stop date, is not complete, but required for the classification, i.e. the occurrence of the AE is not explicitly reported as occurring prior first dose (see eCRF), the AE will be considered treatment emergent.
- Missing assessments of severity, intensity and causal relationship to the IMP will be reported as a separate category.

For the determination of the number of years from start of psoriasis to the screening visit missing starting days will be imputed by the first day of month and missing months will be imputed by the first month (January) of the year.

For concomitant therapies (see section 3.2.2.4) incomplete dates will not be imputed. If an incomplete start or stop date does not allow for the classification as prior and/or concomitant therapy - despite of information in eCRF if taken/used prior to first dosing and/or if ongoing at first dosing - the treatment will be reported as prior and as concomitant therapy.

Pharmacokinetic data below LLQ will be replaced as described in 3.4.7.3 for descriptive statistics and for the derivation of $AUC_{(0,t)}$. Missing pre-dose levels will be imputed by zero. Missing intermediate samples, i.e. missing values in between non-missing levels (quantifiable or substituted by LLQ/2) will be imputed by linear interpolation between the last preceding and the next following available value. The last value will be imputed by LLQ/2, if missing.

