3.5.2 Window for time points

A strict adherence to the visit schedule will be required. Visit schedule violations will be documented as protocol deviations and assessed within the BDRM.

Assessments performed out of the planned visit schedule will be assigned to the nearest, directly preceding or following planned visit, if that visit is missing. If both planned visits are missing and the distances are equal, the assignment is performed to the following one. Otherwise an assessment performed out of the planned visit schedule will not be included in the statistical evaluation and will be listed only.

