3.5.3 Unscheduled visits

If applicable, the reason for unscheduled visit assessments will be given together with the results. For the statistical analysis the unscheduled assessments will be assigned as described in section 3.5.2.

In case of premature withdrawal from the trial, efficacy assessments performed at the time point of withdrawal, will be assigned to a planned visit as described in section 3.5.2.

Safety assessments performed at the time point of withdrawal will be reported together with the last visit in treatment phase (Day 84 / End of Treatment [EoT]).

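### An early-termination PASI or PGA from Day 71 on can become the Week 12 co-primary value, and the SAP's windows and table labels disagree on how such a patient counts

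*Protocol*

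**What the plan says.** **Leaving treatment or trial.** Protocol 5.3.5.2 puts unacceptable symptoms, related serious events and confirmed laboratory limits under the sentence "The following criteria must lead to discontinuation from the clinical trial in individual patients". For patients withdrawn from IMP, the same section says that "the Investigator must make every effort to perform the evaluations described for the End of Treatment and Follow-up Visits", without naming a day. Protocol 5.5.1 has a separate termination visit for patients who leave the trial early, with the Visit 5 procedures (PASI and PGA included): "This visit should take place as soon as possible after the patient stops taking IMP".

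**Which visit the value belongs to.** SAP 3.5.3 says that at premature withdrawal "efficacy assessments performed at the time point of withdrawal, will be assigned to a planned visit as described in section 3.5.2". Under SAP 3.5.2 an assessment outside the visit schedule "will be assigned to the nearest, directly preceding or following planned visit, if that visit is missing". A tie goes to the later visit, but the text states this only for the case where both neighbouring visits are missing. Then: "Otherwise an assessment performed out of the planned visit schedule will not be included in the statistical evaluation and will be listed only".

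**Missing values.** For the primary success rates, SAP 3.5.1 (like protocol 6.6) says that "missing PGA assessments and/or any parts of the PASI assessments will be evaluated as failure to achieve improvement". LOCF is reserved for descriptive analyses up to Day 84. SAP 3.1 defines LOCF as "The last observed value (either scheduled or unscheduled) carried forward and used for all directly subsequent and missing scheduled points". All four primary responder shells (Tables 14.3.3, 14.3.9, 14.3.15 and 14.3.18) carry LOCF in their titles.

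**The Week 12 window.** It is Day 84 +5 in protocol Appendix A, Day 84 ±5 in SAP Table 2, and Days 80 to 91 in the footnotes to Table 14.1.3 part 2. Those footnotes also require at least 80% of planned exposure for completion.

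**The concern.** Both co-primary endpoints are defined at Week 12. A patient who stops early is normally assessed near the stop, so the rules must say whether that assessment is a Week 12 result. Here the answer turns on the calendar day of the stop and on whether the programmer follows the SAP text or the shell titles. An on-treatment result up to 13 days before Day 84 can enter the primary analysis as a response while the disposition table shows the same patient as discontinued before Week 12. A slightly earlier stop with the same clinical result counts as failure. If stops differ between arms in number or timing, these choices feed into the PASI 75 and PGA comparisons.

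**Working it through.** The plan gives no figure for early stops. Its sample size (40 per group, 0.674 against 0.40, two-sided 0.10) reproduces with power 0.801 and does not depend on this point. The check traces the rules by day.

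**Inputs.** Planned visits at Days 56 and 84 (both flow charts); the assignment rule (SAP 3.5.2); the three Day 84 windows; the Table 14.1.3 footnotes; 84 × 2 × 6 planned capsules (SAP 3.4.7.5).

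**Base case.** Days 28 and 56 attended, no Day 84 visit, one termination assessment showing response.

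1. Midpoint between visits: (56 + 84)/2 = Day 70. Days 57–69 are nearer Day 56, and Days 71–83 nearer Day 84. The second run has 83 − 71 + 1 = 13 days.
2. Windows: protocol +5 gives Days 84–89; SAP ±5 gives Days 79–89; the footnote gives Days 80–91. Of the 13 days, 8 (71–78) are outside ±5 and 5 (79–83) inside. All 13 precede the protocol's window.
3. Outcome by day, on the nearest-visit reading:

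| Termination assessment | SAP 3.5.2 | Week 12 (SAP 3.5.1) | In SAP ±5? | Table 14.1.3 part 2, by PASI day |
|---|---|---|---|---|
| Days 57–69 | Day 56 already filled: listed only | failure | no | discontinued |
| Day 70 | equidistant, only one visit missing | unclear | no | discontinued |
| Days 71–78 | Day 84 | response | no | discontinued |
| Day 79 | Day 84 | response | yes | discontinued |
| Days 80–83 | Day 84 | response | yes | completed, if exposure is at least 80% |

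4. Effect of the LOCF label. Take a PGA one point better at a Day 65 termination visit. Under SAP 3.5.1 and 3.5.2 the patient is a failure. Carried forward under the SAP 3.1 definition, the same value is a response. If instead the listed-only value is barred but LOCF is still applied, the Day 56 value decides. The same improvement on Day 72 is a response under either rule.
5. A side issue on counting IMP stops. 84 × 2 × 6 = 1008 capsules, and 80% is 806.4. At 12 capsules a day this is passed on Day 68 (806.4/12 = 67.2). With 5% or 10% of doses missed (assumed), it is Day 71 (806.4/11.4 = 70.7) or Day 75 (806.4/10.8 = 74.7). A patient who stops for an adverse event from then on, stays in the trial, and has PASI within Days 80–91 is a Week 12 completer in Table 14.1.3 part 2. The last days on which such a stop can fall, up to Day 83, number 16, 13 and 9. This takes planned exposure to mean the 1008 capsules.

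**The case against.** **LOCF is confined to descriptive analyses.** On the text this is right: protocol 6.6 and SAP 3.5.1 apply failure to the primary success rates, and SAP 3.5.2 excludes listed-only values from evaluation. The shell label also looks generic, since Table 14.3.3 carries it for Week 16, which is never imputed. A reader might infer that the plan makes LOCF its primary rule; it does not. What stands is that every primary responder shell contradicts the governing text and no shell is labelled with the failure rule.

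**SAP 3.5.2 can be read differently.** If the assessment goes to whichever neighbouring visit is missing, Days 57–70 also become Week 12. The listed-only result is therefore the likelier reading, not a certain one. The alternative does not help: it would let any of 27 days (57–83) supply the Week 12 value.

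**Days 79–83 are on schedule under the SAP.** Correct; the stand-in problem proper concerns Days 71–78. Day 79 shows only that the SAP's window and its disposition footnote disagree.

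**Adverse-event stops are counted.** A reader might infer that no table shows them by arm. The documents do not support that. Both parts of Table 14.1.3 have an adverse-event row by arm, part 2 catches exposure below 80%, Table 14.5.1 counts events leading to study discontinuation, and protocol 5.3.5.2 makes trial exit the default for the listed events. Only the late stopper in step 5 can be missed there, and that patient still appears in the listing planned in SAP 3.4.7.1.

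**Post-stop assessment is requested.** Protocol 5.3.5.2 does ask for every effort at End of Treatment and Follow-up evaluations, so it would be wrong to say that follow-up is abandoned. It does not explicitly ask for a return at Day 84.

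**Conclusion.** The concern holds as an inconsistency in the SAP's handling of Week 12. In the base case, a termination assessment from Day 71 on stands in as the co-primary value, on 8 days outside the SAP's own window and while the disposition footnote calls the patient discontinued. Text and shell labels can turn one termination result into response or failure. The size is a count of days and rules, not an effect. The documents give no stop rate by arm or by day, so neither bias nor loss of power can be stated. The trial is exploratory with descriptive p-values, which limits the consequence, but the rules concern both co-primary endpoints and can be settled before unblinding. The day counts assume that Days 28 and 56 were attended and Day 84 was not; the Days 57–69 result also assumes the nearest-visit reading.

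**What to change.** In the SAP, before database lock:

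- **One window.** Name a single Week 12 window and use it in Table 2, section 3.5.2 and the Table 14.1.3 footnotes.
- **Early assessments.** State that a termination assessment before that window is not used as Week 12 for PASI 75, PASI 50 or PGA response, and that such patients are non-responders.
- **Labels.** Replace LOCF on the responder shells with missing = failure, and say whether a listed-only value may be carried forward in the descriptive LOCF tables.

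Protocol section 6 lets statistical changes before lock be documented in the SAP without an amendment, so the cost is redrafting and reprogramming. The downside is that a few late-stopping patients with an observed response become non-responders.

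Optional: add a by-arm row to Table 14.5.1 for TEAEs leading to discontinuation of IMP, from the action-taken field already recorded under protocol 7.3.1.

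Desirable but separate: ask patients off IMP who have not withdrawn consent and need not leave the trial to return at Day 84. This changes protocol 5.3.5.2, may need a substantial amendment, and is not required for the SAP changes.
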